9.4.4 SAFETY ANALYSES

Please see section 9.4.2 ANALYSIS OF THE PRIMARY EFFICACY ENDPOINT

9.4.5 BASELINE DESCRIPTIVE STATISTICS

Treatments groups will be summarized overall and by clinical site at baseline with regard to demographic characteristics (age, race, ethnicity, and gender), and clinical, laboratory and questionnaire measurements of efficacy (Section 8.1).

9.4.6 PLANNED INTERIM ANALYSES

An O'Brien-Fleming procedure will be used to conduct an interim analysis for safety when 50% of the patients complete the study. A statistical basis for stopping the study at the first look will be achieved if the test statistic for the primary safety endpoint (the occurrence of at least one serious adverse event of grade 3 or higher or the occurrence of thrombocytopenia less than 50,000 per microliter) indicates harm in the NR arm at p \leq 0.003. If the test statistic does not reach p \leq 0.003 at the first look then the trial will proceed to the final analysis. The statisticians (Drs. [name] and [name]) will inform the principal investigator if the interim analysis crosses the boundary in the direction of harm is observed (p \leq 0.003). A treatment effect will be declared harmful at the final analysis if the test statistic indicates harm and p \leq 0.047. The safety data will be summarized at interim analysis. The statisticians will inform the DSMB if there are any safety concerns at the interim analysis. Any decision on stopping the study based on safety will be made in coordination with NIDDK and the DSMB.

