Potential participants who may have severe AKI or advanced CKD will be considered with a binary independent variable in the models addressing this condition with corresponding displays of the line and whisker plots by treatment group and summary tables of coefficients, standard errors and p-values. Interactions between this binary variable and treatment will be of interest and will be described.

Capture and tabulation of concomitant medications, dialysis, co-enrollment in another COVID-19 clinical trial, any new standard of care, pre-existing CKD, and treatments by study arm (NR, Placebo) may be used to define other potential adjustments with binary or categorical variables to be defined post hoc in exploratory analyses. Such models may motivate extended interpretations of any treatment effects found.

PRIMARY END POINT: Safety

All reportable AEs will be listed by Preferred Term by subject, treatment, clinical site, grade, relation to treatment, severity, and seriousness. All unanticipated events will be listed by treatment and clinical site with a detailed description of each event, incident, experience or outcome. An unblinded statistician will summarize safety data periodically for the DSMB.

AEs will be tabulated by treatment and clinical site, displaying, for each event, the number and percentage of participants experiencing at least one Grade 3 or 4 occurrence and he null hypothesis to be tested is H_0 : $p_{NR}=p_{Placebo}$ where p_{NR} and $p_{Placebo}$ are the probabilities of experiencing at least one Grade 3 or Grade 3 event in the NR and Placebo groups. H_0 will be tested with Fisher's Exact test, overall and by clinical site. Additionally, treatment groups will be contrasted on the occurrence at least once of each event with Fisher's exact test. All statistical testing will be two-sided with a significance level of 5%.

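### The final safety level of 0.047 in section 9.4.6 does not belong to the O'Brien-Fleming procedure named there, and sections 9.4.1 and 9.4.2 set 5% for the primary safety test

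*Combined protocol and SAP*

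**What the plan says.** Section 9.4.6 (Planned Interim Analyses) states that an O'Brien-Fleming "procedure will be used to conduct an interim analysis for safety when 50% of the patients complete the study". There is one interim look. The statistical basis for stopping is met if the statistic "indicates harm in the NR arm at p \leq 0.003". If the result does not reach that level "at the first look then the trial will proceed to the final analysis", where harm is declared "if the test statistic indicates harm and p \leq 0.047". The section does not say whether the classical or the alpha-spending form is meant, and it gives no overall level.

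Section 9.4.2, under the primary safety endpoint, compares the arms with Fisher's exact test and closes: "All statistical testing will be two-sided with a significance level of 5" percent. Section 9.4.1 sets the same two-sided 5% for all tests. Section 9.4.4 sends the reader to 9.4.2 for the safety analysis. None of these sections mentions 0.047.

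The event also differs by section:
- Section 9.4.6: "the occurrence of at least one serious adverse event of grade 3 or higher or the occurrence of thrombocytopenia less than 50,000 per microliter".
- Section 9.4.2: the probability of "experiencing at least one Grade 3 or Grade 3 event in the NR and Placebo groups" (the second grade is presumably meant to be 4), with no seriousness condition and no platelet component.
- Synopsis and section 3: a serious adverse event of grade 3 or higher, or a platelet decline of more than 25% from baseline.

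**The concern.** The two levels in section 9.4.6 add to exactly 0.050, which is how a simple additive split would look. An O'Brien-Fleming boundary accounts for the correlation between the two looks and so leaves more for the final test. A statistician who implements the named procedure and one who implements the printed number will use different final thresholds, and one who follows section 9.4.2 will use a third.

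The harm verdict matters beyond the safety tables. In section 2.1 (Rationale for Study Design), all three scenarios for a Phase IIb or Phase III study require that harm is not significantly increased. That rule gives p-value limits for NAD+ (0.05) and for the secondary outcomes (0.2) but none for harm, so it cannot settle which level applies.

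**Working it through.** **Inputs.** Interim level 0.003, final level 0.047, two looks, interim at 50% of patients (section 9.4.6). Final level 5%, two-sided, Fisher's exact test (sections 9.4.1 and 9.4.2). 100 randomized (section 5.5) at 1:1 (section 6.1.1), hence about 25 per arm at the interim and 50 per arm at the end. Assumption: the information fraction t equals the fraction of patients, 0.5.

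**Model.** Z1 (interim) and Z2 (final) are standard normal under no difference, with correlation √t = √0.5 = 0.7071. Overall two-sided error = P(|Z1| > c1 or |Z2| > c2), by numerical integration.

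**The stated pair.** 0.003 gives c1 = 2.968 and 0.047 gives c2 = 1.986. Overall error = 0.0480, against the simple sum 0.003 + 0.047 = 0.050.

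**O'Brien-Fleming at t = 0.5, overall two-sided 0.05.**
- Classical form, c1 = c2/√t: solving gives c2 = 1.977 and c1 = 1.977/0.7071 = 2.797, that is 0.0052/0.0480.
- Spending form, 0.025 on each side: interim spend = 4[1 − Φ(z₀.₉₈₇₅/√t)] = 4[1 − Φ(2.2414/0.7071)] = 4[1 − Φ(3.170)] = 0.0031, so c1 = 2.963. Solving for the final look gives c2 = 1.969, that is 0.0490.
- Spending form applied to the two-sided 0.05 as a whole: 0.0056/0.0478.
- If exactly 0.003 is kept at the interim, the final level that brings the overall error to 0.05 is 0.0490.

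**Attempts to reproduce 0.003/0.047.** One-sided 0.025 gives 0.0026/0.0240 (classical) and 0.0015/0.0245 (spending). One-sided 0.05 gives 0.0088/0.0467 and 0.0056/0.0483. A different information fraction does not help: a final level near 0.047 needs t of about 0.55 (classical) or 0.64 (spending), and the interim level would then be 0.0075 or 0.0102. None of these gives the stated pair.

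**Overall error under each final level, interim 0.003.**

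| Final level | Normal model | Fisher, 25 then 50 per arm, event rates 20–60% |
|---|---|---|
| 0.047 | 0.0480 | 0.025–0.036 |
| 0.049 | 0.0500 | 0.028–0.036 |
| 0.050 | 0.0510 | 0.028–0.036 |

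**Tables that fall between the two final levels.** At 50 per arm, the tables in the harm direction with a two-sided Fisher p above 0.047 and at most 0.05 are 15 v 6 (0.0479), 20 v 10 (0.0486), 40 v 30 (0.0486) and 44 v 35 (0.0479). A level of 0.049 treats all four as the 5% test does. A level of 0.048 counts 15 v 6 and 44 v 35 as harm but not the other two, so the choice of boundary form matters for these tables.

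**Effect on sensitivity, final test alone, 50 per arm, harm direction only.**

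| True rates, NR v placebo | At 0.047 | At 0.05 |
|---|---|---|
| 20% v 20% | 1.23% | 1.41% |
| 30% v 30% | 1.37% | 1.53% |
| 40% v 40% | 1.59% | 1.60% |
| 50% v 50% | 1.76% | 1.76% |
| 40% v 20% | 49.7% | 51.5% |
| 50% v 30% | 46.2% | 46.3% |
| 60% v 40% | 46.2% | 46.2% |

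**The case against.** The strongest reply is that little follows in practice. The stated pair controls the error at 0.0480. Even 0.003 followed by a 5% test gives only 0.0510 in the normal model, and less than 0.05 with Fisher's test. Section 9.4.1 calls the study exploratory and applies no multiplicity correction, and section 9.4.6 leaves any stopping decision to coordination with NIDDK and the DSMB. Only four tables in the harm direction at 50 per arm are affected. All of this stands, and it keeps the point modest.

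It also stands that 0.003 is right to rounding under the spending form, so the interim level is not at fault there. That 0.047 came from subtracting 0.003 from 0.050 is an inference; the documents do not say how it was derived.

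Two stronger readings are tempting, and the documents do not support them:
- A reader might infer that sections 9.4.2 and 9.4.6 test one and the same endpoint at two levels. They share the label of primary safety endpoint, but the events differ, so the two sections could give different p-values from the same patients. The opposite verdicts described here arise only if one event is analysed.
- A reader might take the low chance of a false harm call (1.2% to 1.8%) as proof that 0.047 wastes sensitivity to harm. The rate is almost the same at 0.05. It is low mainly because Fisher's test is discrete and only one direction is counted.

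The reply does not remove the mismatch between name and number, or the absence of any statement on which final level prevails.

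**Conclusion.** The point holds as an inconsistent decision threshold. The final level of 0.047 matches neither the spending partner (0.0490) nor the classical one (0.0480), and it conflicts with the 5% in sections 9.4.1 and 9.4.2. The departure is 0.001 to 0.002 in the conservative direction. Type I error is not inflated, and in the scenarios computed power changes by at most about 1.8 percentage points (51.5% − 49.7%).

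What remains is that a plausible result, such as a doubling from 10/50 to 20/50, would be called harm or not depending on the section consulted, while the go rule in section 2.1 depends on that verdict and names no level. This rests on t = 0.5, on 50 per arm at the end, and on one event definition being used in both sections. With other arm sizes the affected tables change; at the 40 per arm used in section 9.2, for example, 12 v 4 (p = 0.0482) and 9 v 2 (p = 0.0476) fall in the gap.

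**What to change.** 1. In section 9.4.6, name the boundary form and the overall two-sided level, and state one matching pair: 0.003/0.049 for O'Brien-Fleming-type spending, or 0.005/0.048 for the classical form (overall error 0.0500 and 0.0499).
2. In section 9.4.2, replace the 5% for the primary safety test by a reference to that final level, and note the exception in section 9.4.1.
3. In section 2.1, tie the harm condition of the three go scenarios to the same test and level.
4. Reconcile the safety event across the synopsis, section 3, section 9.4.2 and section 9.4.6, so that the single level applies to a single endpoint. Which definition is used is for the sponsor and its clinical advisers to settle.

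Items 1 to 3 cost a few words and need no new data or sample size. They should be made before anyone sees unblinded safety results, because a threshold chosen afterwards would be post hoc.

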1 PROTOCOL SUMMARY

1.1 SYNOPSIS

Title	NIcotinamide Riboside in SARS-CoV-2 pAtients for reNAl protection (NIRVANA)			
Study Description	A pilot, double-blind, placebo-controlled, multicenter, interventional clinical trial with oral nicotinamide riboside (NR) 500 mg (versus placebo) twice daily for a total of 10 days in hospitalized participants with COVID-19.			
Objectives	Primary			
	 To determine the effect of nicotinamide riboside (NR) on whole blood NAD+ levels in hospitalized patients with COVID-19 infection and AKI during the 10-day intervention period; To evaluate the safety of NR in patients with COVID-19 infection and AKI during the 10-day intervention period; 			
	Secondary			
	 To determine the effect of NR on changes in area under curve (AUC) serum creatinine from baseline during the 10-day intervention; To determine the effects of NR on serum creatinine AUC, dialysis, and death with an ordinal categorical outcome having four categories (labeled 1, 2, 3, 4), defined as, in order from least to most severe disease, 1. Serum creatinine AUC < median, 2. Serum creatinine AUC ≥ median, 3. Dialysis, 4. Death during the 90d period post randomization; To determine the effect of NR on MAKE (Major Adverse Kidney Events; composite criteria defined as development or progression of chronic kidney disease, the initiation of long-term dialysis, or death from any cause) at 30d and 90d post randomization; To determine the effect of NR on degree of kidney impairment defined with estimated glomerular filtration rate (eGFR) and proteinuria at 30d and 90d post randomization; 			
	Exploratory			
	• To determine the relationship of whole blood NAD+ levels with AUC creatinine and surrogate markers of AKI such as kidney injury molecule- 1 (KIM-1) and neutrophil gelatinase-associated lipocalin (NGAL);			
Endpoints	Primary			
	 Rates of change in whole blood NAD+ level from baseline to day 10 in NR compared to Placebo. Safety of NR in hospitalized patients with COVID-19 and AKI (defined as the occurrence of at least one serious adverse event of grade 3 or higher or the occurrence of thrombocytopenia (>25% decline in blood platelet count from baseline value). 			

	Secondary				
	 Rates of change in AUC serum creatinine benchmarked to baseline from baseline to day 10 in NR compared to Placebo; An ordinal categorical outcome with four categories (labeled 1, 2, 3, 				

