3 OBJECTIVES AND ENDPOINTS

OBJECTIVES	ENDPOINTS	JUSTIFICATION FOR		
		ENDPOINTS		
Primary				
 To determine the effect of nicotinamide riboside (NR) on whole blood NAD+ levels in hospitalized patients with COVID-19 infection and AKI during the 10-day intervention period; To evaluate the safety of NR in patients with COVID-19 infection and AKI during the 10-day intervention period. 	 The primary endpoint is the rate of change in whole blood NAD+ level over the 10 day period from baseline to day 10. Safety of NR in hospitalized patients with COVID-19 and AKI (defined as the occurrence of at least one serious adverse event of grade 3 or higher or the occurrence of thrombocytopenia defined as >25% decline in blood platelet count from baseline. 	 Recent clinical data indicate a reduction of blood NAD+ level in AKI patients and an increase in NAD+ in 48 hrs with NR treatment; The safety of NR in COVID-19 patients is not known 		
Secondary	-	-		
• To determine the effect of	• The rate of change in AUC	• The recovery of AKI, as		
NR on changes in AUC	benchmarked to baseline;	assessed by AUC serum		

Table 2: Study objectives, endpoints, and justification for endpoints

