5.2 EXCLUSION CRITERIA

An individual who meets any of the following criteria will be excluded from participation in this study:

- 1. Hypersensitivity to nicotinamide riboside (NR);
- 2. Pregnant or lactating women confirmed with positive laboratory pregnancy tests as per local requirements;
- eGFR <15 mL/min/1.73 m² as per the Chronic Kidney Disease Epidemiology Collaboration equation at admission lab;
- 4. Maintenance renal replacement therapy or initiation of renal replacement therapy before randomization
- 5. Currently on NR or nicotinamide or vitamin B3 (niacin) supplementation (multivitamins are allowed);
- 6. Concomitant cirrhosis of liver or acute liver failure;
- 7. Any medical history or condition that might, in the opinion of the attending physician, put the participant at significant risk if he/she were to participate in the trial;
- 8. Individuals with kidney transplant;
- 9. Individuals with blood platelet count <100,000/microL;

Rationale: The exclusion criteria are primarily designed for patient safety. In addition, these exclusion criteria address some uncertainties in the COVID-19 severity and effects of concomitant medications on disease progression. For example, the incidence of AKI in kidney transplant recipients with COVID-19 is not well studied [73]. Moreover, kidney transplant recipients are on maintenance immunosuppressive therapy with deleterious effects on infection

outcomes. An optimal management of immunosuppressive agents in this patient group with COVID-19 is not clear [74].

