8.3.4 TIME PERIOD AND FREQUENCY FOR EVENT ASSESSMENT AND FOLLOW-UP

The study investigators will assess and record all events with start dates occurring any time after informed consent is obtained until Day 90 – the last visit. The study investigator will review EHR daily to collect and assess all AEs (including SAEs) from the time participants provided consent to the study until Day 10 and again during Day 30 and Day 90 follow-up visits regardless of its relationship to study drug. At each visit, the investigator will inquire about the occurrence of any new and the prognosis of already documented AE/SAEs since the last visit. All AEs will be captured in detail and followed to satisfactory resolution or stabilization, until the investigator deems the event chronic or not clinically significant and until the participant is considered to be stable. The participants will receive standard of care for the events. Site investigators will also assess if there is a reasonable possibility that the study drug or procedure caused the event. Investigators will also consider if the event is explained by the participant's underlying medical conditions, anticipated clinical course, previous medical conditions, and concomitant medications.

Routine and safety laboratory values from the respective hospital laboratories will be reported by each site investigator to the SAC as soon as the results are available to the study database. Participants will receive standard of care for the event and followed to satisfactory resolution or stabilization, The DCC will review laboratory results for completeness. Any abnormal laboratory test results (clinical chemistry, hematology, or urinalysis) or other safety assessment (e.g., CPK), including those that worsen from the baseline, felt to be clinically significant in the medical and scientific judgement of the investigator, will be recorded as AEs. The SAC will review AEs weekly and SAEs on a daily basis and any events that the clinical centers categorize as requiring treatment discontinuation for safety reasons.

The following laboratory results will be flagged as expected study AEs in this trial:

- Thrombocytopenia: Platelet count >25% reduction from the baseline;
- Liver function test abnormalities: AST, ALT, total bilirubin, alkaline phosphatase > 4 times the upper limit of normal;
- Creatinine phosphokinase (CPK): > 4 times upper limit of normal;

The following symptoms will be flagged as expected study AEs in this trial:

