8.3.6 SERIOUS ADVERSE EVENT REPORTING

The study investigators will report all unexpected serious adverse events and their relatedness to study drug or procedure to the DCC within 24 hours of awareness or initial assessment. The DCC will then notify the sIRB and NIDDK. These reporting will follow the criteria outlined in 21 CFR 312.32(c). The SAC will be blinded to the randomization code and will determine if the event is unexpected and define the relationship to NR based on section 8.3.3.2. An adverse event is considered "unexpected" if it is not listed in the study protocol (21 CFR 312.32(a)). If a determination is made that a serious adverse event which is not exempt and has a reasonable possibility of having been caused by a study procedure or the study drug, it will be classified as a suspected adverse reaction. If the suspected adverse reaction is unexpected, it will be classified as a SUSAR.

The DCC will report all unexpected deaths, serious and treatment related adverse events, and SUSARs to the DSMB and NIDDK within 7 working days after receipt of the report from a

clinical site. A written report will be sent to the DSMB, FDA, local IRB, and the sIRB within 15 calendar days. The DSMB will also review all reported adverse events and clinical outcomes during scheduled DSMB meetings. The DCC will distribute the written summary of the DSMB's periodic review of reported adverse events to the local IRB and sIRB in accordance with NIH guidelines (*http://grants.nih.gov/grants/guide/notice-files/not99-107.html*).

In addition, (1) serious, unexpected suspected adverse reactions, (2) findings from other clinical, animal, or in-vitro studies that suggest significant human risk, and (3) a clinically important increase in the rate of a serious suspected adverse reaction will be reported to all investigators, sIRB, local IRB, the FDA, and the DSMB no later than 15 calendar days after determining that the information qualifies for reporting [21 CFR 312.32(c)(1)].

Clinical Outcomes that will be Exempt from Serious Adverse Event Reporting

Pre-specified laboratory safety endpoints will be designated to evaluate possible laboratory abnormalities that might be seen with NR based on previous studies with NR (i.e., <10% reduction in hemoglobin and >25% reduction in platelet counts from baseline).

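### The harm boundaries in 9.4.6 apply to a different safety event from the one in the endpoint tables, and the overall safety test in 9.4.2 uses a third

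*Combined protocol and SAP*

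**What the plan says.** **Event.** The synopsis (1.1) defines the primary safety endpoint as a serious adverse event of grade 3 or higher, or "the occurrence of thrombocytopenia (>25% decline in blood platelet count from baseline value". Table 2 in section 3 has the same two parts, the second being "the occurrence of thrombocytopenia defined as >25% decline in blood platelet count from baseline". Section 8.3.4 flags the same relative criterion as an expected adverse event ("Thrombocytopenia: Platelet count >25% reduction from the baseline"), and 8.3.6 lists it among the laboratory safety endpoints ("<10% reduction in hemoglobin and >25% reduction in platelet counts from baseline").

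Section 9.4.6 says that it tests the primary safety endpoint and keeps the serious-event part, but its platelet part is "the occurrence of thrombocytopenia less than 50,000 per microliter".

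Section 9.4.2 tabulates, for each event, "the number and percentage of participants experiencing at least one Grade 3 or 4 occurrence". Its overall null hypothesis compares the probabilities of "experiencing at least one Grade 3 or Grade 3 event in the NR and Placebo groups", where the repeated grade is presumably a slip for Grade 4. It also tests each event separately. Section 9.4.4 only refers back to 9.4.2.

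**Final level.** Section 9.4.6 declares harm at p ≤ 0.047. Section 9.4.2 tests safety, and 9.4.1 tests everything, at a two-sided 5%.

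**Who is told.** Under 9.4.6 the statisticians inform the principal investigator if the harm boundary is crossed, and stopping is decided with NIDDK and the DSMB. Section 5.5 describes a pause after 50 participants for DSMB review of primary outcome data. NIDDK then decides on the DSMB's recommendation, and investigators stay blinded.

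**The concern.** A stopping boundary and a final harm test have meaning only for a defined event. Here one name covers two platelet criteria that are far apart, and the section that specifies the final test describes a third event. Each of the three scenarios for further development in 2.1 requires no significant increase in harm. The plan does not settle which comparison answers that, and the choice could be made after the data are seen.

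The platelet part is not peripheral. Section 2.3.1 reports a small but statistically significant platelet fall with NR in healthy volunteers, and transient thrombocytopenia with nicotinamide in hemodialysis patients.

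**Working it through.** **The plan's own figures.** For two looks at half information under normal theory, O'Brien-Fleming-type spending with 0.025 per side gives a first-look level of 0.00305, which matches 0.003. The three O'Brien-Fleming variants tried give final levels of 0.0490, 0.0480 and 0.0478. None gives 0.047, which equals 0.050 − 0.003, a simple additive split. The stated pair is on the conservative side, and the point does not rest on it.

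**The three events side by side.**

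| Feature | Synopsis, Table 2 | 9.4.6 | 9.4.2 overall test |
|---|---|---|---|
| Seriousness required | yes | yes | no |
| Grade | 3 or higher | 3 or higher | 3 or 4 |
| Platelet part | fall >25% from baseline | count <50,000 per microliter | none |

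**How far apart the platelet parts are.** Section 5.2 excludes "Individuals with blood platelet count <100,000/microL". Taking the baseline count B as at least 100,000, a count below 50,000 is a fall of more than 1 − 50,000/B, so more than 50% at B = 100,000 and more than 75% at B = 200,000. A fall from 200,000 to 140,000 is 60,000/200,000 = 30%: it is an event in the endpoint tables and not in 9.4.6. (The 200,000 is illustrative. Section 5.2 does not time the eligibility count, so the 100,000 floor at Day 1 is an inference.)

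**Effect on the verdict.** Inputs: 100 randomized (5.5), 1:1 (6.1.1), so 50 per arm; 25 per arm assumed at the interim; two-sided Fisher's exact test (9.4.2); levels from 9.4.6. Assume b participants per arm have a serious event of grade 3 or higher, and k further NR participants have only a fall above 25%, with a count of at least 50,000. The endpoint-table event then compares b + k with b, and the 9.4.6 event compares b with b (p = 1.0). The smallest k that reaches the level is:

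| Look | b | k | NR v placebo | p |
|---|---|---|---|---|
| Final, 0.047 | 5 | 9 | 14 v 5 | 0.0395 |
| Final, 0.047 | 10 | 11 | 21 v 10 | 0.0297 |
| Final, 0.047 | 15 | 11 | 26 v 15 | 0.0414 |
| Final, 0.047 | 20 | 11 | 31 v 20 | 0.0449 |
| Final, 0.047 | 25 | 11 | 36 v 25 | 0.0397 |
| Interim, 0.003 | 5 | 12 | 17 v 5 | 0.0014 |

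At the final look, k of 9 to 11 is 18 to 22 percentage points of 50.

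**Deaths.** Section 8.3.3.1 grades death as 5. At the 9.9% mortality that 2.2 gives for patients meeting the trial's criteria (time window not stated), about 100 × 0.099 ≈ 10 deaths are expected. The other rates quoted, for broader or sicker groups, run from 7.6% (2.2) to 52% (4.2), or about 8 to 52 per 100. Only deaths without a Grade 3 or 4 event would be missed in 9.4.2. The documents do not allow that number to be estimated.

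**Final level.** At 50 per arm, four tables with NR worse have 0.047 < p ≤ 0.05: 15 v 6 (0.0479), 20 v 10 (0.0486), 40 v 30 (0.0486) and 44 v 35 (0.0479). The chance of landing on one is 0.0017 at 20% v 20%, 0.0016 at 30% v 30%, 0.0183 at 40% v 20% and 0.0224 at 30% v 12%.

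**Overall error with the planned test.** Enumerating 25 then 50 per arm with Fisher's test at 0.003 and 0.047 and equal event rates of 10%, 20%, 30% and 50% gives an overall two-sided error of 0.018, 0.025, 0.028 and 0.036.

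**Crossing the interim boundary.** At 25 per arm, with 0 to 16 placebo events, an NR excess of 9 to 12 participants is needed (for example 9 v 0, p = 0.0016), that is 36 to 48 percentage points.

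**The case against.** The illustration is one-sided by construction: every isolated platelet fall is on NR, and the serious-event counts are identical. That stands. It shows that the verdicts can diverge, not that they are likely to. A platelet excess would also not go unseen, because 9.4.2 tests each event separately and the DSMB reviews adverse events. Those tests are not the declared primary safety comparison, however, and they do not drive the 9.4.6 boundary.

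On the level, the specific rule in 9.4.6 would normally override the general 5%. A reader might infer that two final levels inflate the false-positive rate. The documents do not support that: with Fisher's test the overall error stays well below 0.05. The effect is confined to four borderline tables.

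On reporting, a reader might infer that 9.4.6 flatly contradicts 5.5, or that it unblinds participants. Neither follows. The blinding sentence in 5.5 concerns the review after 50 participants, which may not be the 9.4.6 look. A crossing notice discloses the direction of a group difference, not assignments. The notice goes to the principal investigator, whereas 8.3.4 gives causality judgements to site investigators. The endpoint counts events regardless of relatedness, and the adjudicators are masked. What remains is an unnecessary disclosure in a blinded trial.

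Whether 5.5 and 9.4.6 describe one look or two is unclear, but both can be followed as written, so this calls for clarification and is not an error.

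**Conclusion.** The mismatch in the safety event is established on the text alone. Sections 1.1 and 3 agree with each other, 9.4.6 uses a stricter platelet criterion under the same name, and the overall test in 9.4.2 omits platelets, drops seriousness and stops at Grade 4. Its possible effect is a reversal of the harm verdict, such as p = 0.030 against p = 1.0. That size rests on 50 per arm, equal serious-event counts, isolated falls on NR only, and the 9.4.6 level applied to the endpoint-table event, since those tables state no level.

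The final-level and reporting points are minor. The first changes the classification of four tables at 50 per arm. The second matters only if the boundary is crossed and the trial continues. The documents do not show which platelet criterion was intended, and none is favoured here.

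**What to change.** (a) Reconcile the synopsis, Table 2, 9.4.2 and 9.4.6 to one safety event. State the platelet criterion (the team's choice), whether seriousness is required, and whether Grade 5 counts. Use that event for the interim boundary, the final test and the harm condition in 2.1. Correct the repeated grade in 9.4.2.

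(b) Minor: add a sentence to 9.4.2 saying that the primary safety comparison uses the final level in 9.4.6 instead of the general 5%. The consequence is that the four borderline tables are classed as not harmful. No other level is proposed, because the planned test is already conservative.

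(c) Minor: in 9.4.6, have the unblinded statisticians report a crossing to the DSMB, with NIDDK acting on the DSMB's recommendation as in 5.5, and delete the step informing the principal investigator. Nothing needed to act is lost, because 9.4.6 already places stopping decisions with NIDDK and the DSMB.

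(d) Clarification: say whether the 5.5 review and the 9.4.6 test are the same look.

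The cost is wording in these sections and a cross-reference in 5.5, with no added participants, visits or assays. The event should be settled before any unblinded safety comparison is made.
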